2 ASSESSMENT CHART

2.1 STUDY DESIGN

2.1 ASSESSMENT CHART

Study period	Run-in*		Period I (double-blinded)		Period II (follow-up)	
	V1	V2	V3	V4	V5	V6
Visit	V1	V2	V3	V4	V5	V6
Time (weeks)	-2	0	2	4	8	16
Informed consent	X					
Inclusion/Exclusion criteria	X					
Demography/Medical history	X					
Physical examination	X	X		X	X	X
Randomization		X				
TSS, TNSS, TOSS, TTSS		X	X	X		
VAS		X	X	X		
PRQLQ		X		X	X	X
Incidence, intensity, and duration of exacerbations					X	X
Use of rescue medication			X	X	X	X
Provide/return diary		X	X	X	X	X
Dispensation of double blind treatment		X				
Dispensation of Lertal				X		
Concomitant treatment		X	X	X	X	X
Adverse Event monitoring		X	X	X	X	X
Product accountability			X	X	X	X

* Visit 1 and Visit 2 may take place on the same day.

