6.2 SECONDARY

The secondary objective is to evaluate efficacy, safety and quality of life in pediatric patients with allergic rhinoconjunctivitis treated with Lertal[®]. The secondary endpoints are the following:

- Overall symptom control assessed by means of a VAS after 2 and 4 weeks of treatment.
- Change from baseline of the Total Symptom Score (TSS) after 2 weeks of treatment.
- Number of responders (at least 30% reduction of TSS) after 2 and 4 weeks of treatment.
- Time to maximum effect on TSS vs placebo.
- Use of “rescue treatment.”
- Change from baseline of Total Nasal Symptom Score (TNSS) after 2 and 4 weeks of treatment.
- Change from baseline of Total Ocular Symptom Score (TOSS) after 2 and 4 weeks of treatment.
- Change from baseline of Total Throat Symptom Score (TTSS) after 2 and 4 weeks of treatment.

- Issues interfering with quality of life at Baseline (Week 0), after Period I (Week 4) and after Period II (Week 8 o Week 16).
- Number of patients symptom-free or with mild symptoms during Period I.
- Number, intensity and duration of exacerbations during Period II. Exacerbations are defined as the need of an antihistamine medication of any kind, at any dose and of any duration.

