7 STUDY DESIGN

7.1 DESCRIPTION OF THE PROTOCOL

❖ Run-in

The 2-week run-in period consists of two visits: Visit 1 at Week -2 and Visit 2 at Week 0. Visit 1 and Visit 2 may be performed on the same day. During these visits, after having obtained signed informed consent from the patient, the Investigator will gather demographic and medical history data, perform a physical examination of the patients and evaluate their eligibility for the study according to inclusion/exclusion criteria indicated in [Section 8](#). Eligible patients will then be randomized in a 1:1 ratio into two treatment groups and will be dispensed one of the study treatments:

- Lertal® double-layer tablets (1 tab/day for 4 weeks) plus standard therapy (antihistamine).

or

- Lertal® placebo tablets (1 tab/day for 4 weeks) plus standard therapy (antihistamine).

The randomization list will be stratified by type of allergy (pollen or dust mites).

Baseline assessments of patient reported outcomes (PRO) will be collected at Visit 2 (Week 0). The patient will also be given a diary on which to record the use of rescue medication/concomitant medication and the occurrence of adverse events. The diary will also be used to record the occurrence/duration of exacerbations during Period II (need of an antihistamine medication of any kind, at any dose and of any duration).

❖ Period I

Visit 3 (Week 2) and Visit 4 (Week 4) constitute the 4-week double-blinded treatment period (Period I). During these visits, patients will be asked to complete their questionnaires and to return their diaries so information concerning safety (adverse events) and the use of rescue/concomitant medications can be collected. Patients need to return all unused product at both visits to check compliance with treatment. Once all data entry related to Period I has been completed (the Investigator has to certify that the data entered are complete and accurate), the eCRF will make the unblinding procedure available to the investigator so he or she can find out what treatment was

taken by the patient during the double-blinded period. All assessments scheduled for Visit 4 shall be performed prior to unblinding.

A patient that concludes treatment Period I and still presents symptoms that do not permit interruption of standard therapy is considered a non-responder and will not take part in Period II of the study. The patient will be discontinued from the study.

❖ Period II

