Period II is a 4-week (pollen allergy) or 12-week (dust mite allergy) open-label, parallel-group, extension study in which patients treated with study product during Period I continue treatment with Lertal[®] tablets, whereas patients initially treated with placebo receive no further treatment. Two visits, Visit 5 – Week 8 and Visit 6 – Week 16 (the latter only for patients with dust mite allergies) are scheduled during this period to collect efficacy, safety and quality of life data. Patients should return their diaries at these visits in order to collect data concerning exacerbations and or adverse events. Patients also need to return all unused product to check compliance with treatment.

See [Section 2](#) for a graph of the study design and a table of what assessments are to be carried out and when. See [Section 10](#) for a description of the assessments.

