13.2.2 Statistical Analysis

All data collected in the study will be listed and summarized as appropriate as described below. Continuous data will be summarized by means of common descriptive statistics: mean, standard deviation (SD), median, first and third quartiles, minimum and maximum. Categorical data will be presented by absolute and relative frequencies (n and %) or contingency tables.

For the safety analysis, patients will be included in based on available assessments; no missing data handling approach will be applied. For efficacy analyses, patients who interrupt treatment will be considered as “failures” for qualitative variables and their missing quantitative data will be substituted according to the LOCF method (Last Observation Carried Forward). Unless stated otherwise, two-sided p-values <0.05 will be considered statistically significant.

All statistical tables, listings, figures and analyses will be generated using SAS® release 9.4 or later (SAS Institute Inc., Cary NC, USA).

No interim analyses are planned.

Further details about data analysis will be provided in the Statistical Analysis Plan document.

All data about patient demographics and baseline characteristics will be summarized on the ITT population by treatment group by means of summary descriptive statistics.

The number and percentages of subjects meeting all eligibility criteria at screening will be provided. The analysis populations will be described and the reasons for excluding a patient from any particular population will be provided with the number of protocol deviators per each criterion.

A complete description of patients’ disposition will be provided specifying the number of randomized patients, the number of patients at each visit, the number of completed and discontinued patients and the reason for the discontinuation.

Medical history data will be presented by Medical Dictionary for Regulatory Activities MedDRA dictionary system organ class (SOC) and preferred term (PT).

Concomitant medications and significant non-drug therapies will be presented by WHO Drug Dictionary ATC class and preferred term.

- **Primary endpoint**

Changes from baseline of TSS scores will be calculated after 4 weeks of treatment. The between-group analysis will be performed by means of a t-test for independent samples or analogous non-parametric test.

- **Secondary endpoints**

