- Change from baseline of VAS score after 2 and 4 weeks of treatment. The between-group analysis will be performed by means of a t-test for independent samples or analogous non-parametric test.

- Changes from baseline of TSS scores after 2 weeks of treatment. The between-group analysis will be performed by means of a t-test for independent samples or analogous non-parametric test.
 - Changes from baseline of TSS score for each patient after 2 and 4 weeks of treatment will be classified as $\geq 30\%$ and $< 30\%$, thus defining responder and non-responder patients. Between-group differences will be tested by means of a Chi-square test with 2x2 contingency tables.
 - Time to maximum effect on TSS vs placebo will be analysed by means of t-test for independent samples after log-transformation of the data or analogous non-parametric test.
 - Between-group differences in the number of patients using rescue treatment will be analyzed by means of a Chi-square test with 2x2 contingency tables.
 - Changes from baseline in TNSS, TOSS and TTSS scores will be calculated after 2 and 4 weeks of treatment and between-group differences analyzed by means of a t-test for independent samples or analogous non-parametric test.
 - The number of patients with score for a single symptom ≤ 1 will be calculated and the between-group differences analyzed by means of a Chi-square test with 2xn contingency tables, where n represents the number of observations.
 - The intensity of the onset of exacerbations occurring during Period II will be evaluated through the TTS score and compared between the two groups using a t-test for independent samples or analogous non-parametric test.
 - The between-group differences in the number and duration of exacerbations occurring during Period II will be analyzed by means of a Mann-Whitney U test.
- **Quality of life**

Changes from baseline of the PRQLQ total score will be calculated at the end of Period I (Week 4) and end of Period II (Week 8 or Week16). An analysis of variance for repeated measures will be adopted, isolating the variability due to type of allergy, treatment group, time of observation and their interaction.

- **Safety**

All safety analyses will be performed on the Safety set. No missing data handling approach will be applied.

Results of physical examinations at each assessment will be presented.

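### The planned Mann-Whitney test of Period II exacerbation number and duration can use only children able to stop standard therapy at Week 4, a post-randomisation subset, and it ignores the allergy stratum that sets follow-up length

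*Combined protocol and SAP*

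**What the plan says.** **Entry to Period II.** A patient who, when Period I is over, "still presents symptoms that do not permit interruption of standard therapy is considered a non-responder and will not take part in Period II" (Section 7.1; likewise Sections 1 and 9.1). Sections 7.1 and 11.2.2 say that this child is discontinued from the study. Section 11.2.3, in contrast, follows patients who permanently stop treatment up to their scheduled study completion.

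**Endpoint.** "Exacerbations are defined as the need of an antihistamine medication of any kind, at any dose and of any duration" (Section 6.2). In the Section 2 assessment chart, the row "Incidence, intensity, and duration of exacerbations" is marked at Visits 5 and 6 only.

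**Analysis.** Section 13.2.2 says that differences in "number and duration of exacerbations occurring during Period II will be analyzed by means of a Mann-Whitney U test". It names no Period II analysis set, no stratification and no allowance for follow-up length. Efficacy uses the ITT set. Children who interrupt treatment are failures "for qualitative variables and their missing quantitative data will be substituted according to the LOCF method".

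**Stratum and follow-up.** Randomisation is stratified by allergy type (Sections 7.1 and 9.4). Period II is a "4-week (pollen allergy) or 12-week (dust mite allergy) open-label, parallel-group, extension study" (Section 7.1). Only the PRQLQ model uses allergy type.

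**What is already planned.** Section 9.10 counts any antihistamine use in Period II as rescue, and Section 13.2.2 compares the number of rescue users by chi-square. Disposition will give "the number of patients at each visit, the number of completed and discontinued patients and the reason for the discontinuation". Further analysis detail is left to the Statistical Analysis Plan.

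**The concern.** An exacerbation is the need for an antihistamine, yet the children known still to need one at Week 4 are those left out of the comparison. Their status is fixed after four weeks of randomised treatment. If the product changes who can stop, the two groups of entrants are no longer alike.

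Number and duration of exacerbations are the trial's evidence on lasting control once the antihistamine is withdrawn. Under a simple model in which the product lowers Week-4 severity by a constant amount, more of the severe children enter on Lertal, and a real Period II benefit is partly hidden. A reversed Week-4 effect would flatter Lertal.

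Separately, mite-allergic children are observed three times as long as pollen-allergic children (12 against 4 weeks). An unstratified rank test treats that difference as noise.

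**Working it through.** **Step 1. Can the stated missing-data rules fill the gap?** A non-entrant has no earlier exacerbation count or duration, because the endpoint does not exist before Week 4. LOCF therefore supplies nothing. The failure rule covers qualitative variables only. Unless Section 11.2.3 prevails, the Mann-Whitney test can use entrants only. If it does prevail, the plan still lacks a rule for turning continued antihistamine use into a number or duration of exacerbations.

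**Step 2. The plan's own figure.** Section 13.1 gives 72 per group for an effect of 0.47 SD, 80% power and two-sided 5%. An exact t-test calculation gives 79.98% power at 72, so the figure reproduces. It concerns Week-4 TSS; no figure is given for exacerbations.

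**Step 3. Size of the selection effect on counts.** The documents give no entry rate, exacerbation rate or correlation, so everything here is assumed. Untreated severity U is standard normal. The Week-4 score has correlation r with U and is shifted by -d on Lertal. A child enters if the score is below c. The log exacerbation rate has slope b in U. With no Period II effect, the entrants-only rate ratio, Lertal to placebo, is

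[Φ(c+d-rb)/Φ(c+d)] / [Φ(c-rb)/Φ(c)].

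Take d = 0.47 (the TSS effect of Section 13.1, applied by assumption to the decision to stop), r = 0.7 and b = 1.

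- c = 0.5: entry is 69.15% on placebo and 83.40% on Lertal. Ratio = (0.6064/0.8340)/(0.4207/0.6915) = 0.727/0.608 = 1.20. Children without a value: 80 × (0.3085 + 0.1660) = 38 of 160.
- c = 0: entry is 50% and 68.08%. Ratio = (0.4090/0.6808)/(0.2420/0.5000) = 0.601/0.484 = 1.24. Without a value: 80 × (0.5000 + 0.3192) = 66 of 160.

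Over r = 0.5, 0.7, 0.9 and b = 0.5, 1, the ratio runs from 1.06 to 1.33. With d = -0.47 it runs from 0.73 to 0.93. With d = 0 it is 1.00.

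**Step 4. Rejection rates.** Simulation with 80 per arm, 48 mite and 32 pollen (the 60% mite limit of Section 9.4 taken as the split), Poisson counts averaging 0.15 per week, no other dropout, two-sided 5%, r = 0.7, b = 1. Yes/no means antihistamine needed after Week 4, with non-entry counted as yes, tested by Cochran-Mantel-Haenszel. Paired values are for placebo entry 69% / 50%.

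| Case | Planned test | Stratified rank test | Yes/no, all ITT |
|---|---|---|---|
| No effect in either period | 4.3% / 4.6% | 5.0% / 5.1% | 5.0% / 5.0% |
| Period I effect only | 7.2% / 8.0% | 8.6% / 9.1% | 9.8% / 19.0% |
| 40% Period II reduction only | 29% / 20% | 32% / 22% | 18% / 12% |
| 0.47 SD and 40% reduction | 18% / 11-12% | 20% / 12-13% | 49-50% / 54-55% |

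In the second row, only 0.6% / 0.7% of trials favour Lertal. With the Week-4 effect reversed and no Period II effect, the planned test favours Lertal in 7.4% / 6.5% of trials, against a nominal 2.5%. In the last row, varying r and b moves the planned test between 9% and 45%, and yes/no between 48% and 65%.

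**Step 5. A different model.** With gamma-distributed severity, 0.1 exacerbations per week and entry of 60% placebo against 80% active, mean counts with no Period II effect were 0.54 and 0.69. Rejection was 9.6% (planned) and 10.9% (stratified). At a true rate ratio of 0.6, the planned test had 25% power with equal 70% entry and 8.7% with 60% against 80%.

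**The case against.** **Much is already planned.** Period II rescue is any antihistamine use, in substance the exacerbation definition, and a yes/no test of rescue use is specified. A reader might infer that the plan has nothing for the excluded children; that is not so. What stands is narrower. The rescue test is not split by period, and since non-responders do conclude Period I, it is unclear whether the failure rule covers them. Nor is non-entry untracked: Section 11.2.2 names the non-responder and asks for reasons on the eCRF, and Section 13.2.2 reports reasons. Only a split by arm and allergy type is unstated.

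**The stratum matters little.** A reader might infer that ignoring 4- against 12-week follow-up inflates false positives. It does not: the planned test rejects in 4.3% / 4.6% with no effect. Stratifying gains about 1-3 points of power centrally, does not remove selection, and rejects slightly more often under it.

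**Sections 11.2.2 and 11.2.3 may keep these children under follow-up.** This stands as an unresolved conflict, and the premise depends on it.

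**The sizes are assumed.** True. They also cover counts only; duration was not quantified. The structural gap in Step 1 needs none of these numbers.

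**Conclusion.** The point holds at minor to moderate weight, for secondary endpoints only. The primary endpoint and sample size are unaffected. Under the stated entry rule, number and duration of exacerbations are compared in a subset chosen by a post-randomisation outcome, and nothing in Section 13 says so or provides for it.

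A reader might go further and infer that the comparison is biased in a known direction. The documents do not support that. The direction depends on whether and how the product changes Week-4 status, on a constant shift, and on one severity factor common to both periods. With no Week-4 effect the ratio is 1.00, provided the decision to stop therapy is made before unblinding. Section 7.1 places Visit 4 assessments before unblinding, but the assessment chart has no separate item for that decision. The simulations also leave out other dropout (Section 13.1 expects 12%) and open-label knowledge in Period II, which could act either way.

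**What to change.** First reconcile Sections 7.1 and 11.2.2 (discontinued from the study) with Section 11.2.3 (followed to scheduled completion), because this decides whether these children have Period II data. Then, in the SAP:

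1. Stratify the entrants-only rank test by allergy type (van Elteren). State that this does not remove selection and rejects slightly more often under it (about 9% against 7-8% in the central assumed case).
2. Describe that comparison as conditional on stopping standard therapy at Week 4, not as a randomised treatment effect.
3. Build on the rescue-use test already planned instead of adding an endpoint. Report Period II antihistamine use (yes/no) for all ITT children, count symptom-related non-entry at Week 4 as failure, state how children leaving for other reasons are counted, and test by Cochran-Mantel-Haenszel stratified by allergy type.
4. Split the planned disposition counts and discontinuation reasons by arm and allergy type.

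The cost is SAP wording, two stratified tests in place of unstratified ones, and a split of a planned table. Items 3 and 4 rely on the eCRF discontinuation reason, so a coded reason may have to be added. Item 3 has a price that the SAP should state: it mixes Period I and Period II effects (10% / 19% rejection when only a Period I effect exists) and has low power for a pure Period II effect (18% / 12% for a 40% reduction). No change to clinical management is proposed.

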7.2 DURATION OF STUDY PARTICIPATION

7.2.1 Duration of study participation for each patient

The study for each participant will last approximately 10 weeks for patients allergic to pollen and 18 weeks for patients allergic to dust mites.

7.2.2 Determination of end of clinical trial (all patients)

The study will end with the last visit of the last patient.

8 SELECTION OF PATIENTS

The study population will be made up of children affected by allergic rhinoconjunctivitis. The study will be conducted at approximately 17 sites located in Italy.

8.1 INCLUSION CRITERIA

Each patient must meet all of the following inclusion criteria:

- Age 6 to 12 years
- Male or female
- Diagnosis of allergic rhinoconjunctivitis

- Hypersensitivity to dust mites or pollen confirmed with skin-prick test (wheal and redness, ≥ 3 mm more extended than control) performed in the previous 12 months
- Total Symptoms Score (TSS) ≥ 15 and at least 1 for nasal congestion
- Written informed consent of patient and of parent or legal guardian

8.2 EXCLUSION CRITERIA

Each patient must meet none of the following exclusion criteria:

- Uncontrolled asthma
- Secondary rhinitis to other causes
- Documented evidence of acute or chronic sinusitis
- Nasal polyps
- Chronic or intermittent use of inhaled, oral, intramuscular, intravenous or topical corticosteroids
- Use of leukotriene antagonists
- Continuous use of antihistamines
- Inadequate washout of drugs:
 - Systemic or intranasal corticosteroids: 1 month
 - Leukotriene antagonists: 1 month
 - Sodium cromoglycate: 2 weeks
 - Systemic or intranasal decongestants: 3 days
 - Cetirizine, fexofenadine, loratadine, desloratadine, hydroxyzine: 5-10 days
- Malformations of the nose, ear or throat
- Upper or lower respiratory tract infection in the last 2 weeks
- Participation in other clinical studies in the last month
- Documented hypersensitivity to the study product or its excipients
- Trip planned outside of the study area

9 STUDY TREATMENTS

9.1 INVESTIGATIONAL PRODUCT

Lertal® double-layer tablets

Lertal[®] is a novel food supplement. Each tablet contains the following active ingredients in a double-layer “fast-slow” release tablets:

- Quercetin 150 mg: a natural flavonoid that inhibits the release of histamine, leukotrienes, PGD2, IL (IL-6, IL-8, TNF-alpha).
- *Perilla frutescens* 80 mg: A dry extract of the seeds containing rosmarinic acid, luteolin, apigenin and crysoeriol that inhibits the release of histamine and expression of interleukins (IL-6, TNF-alpha).
- Vitamin D3 5 mcg (200 IU), which contributes to the normal function of the immune system.

One oral Lertal[®] tablet a day is to be administered together with standard therapy (antihistamine) for 4 weeks by patients randomized to the active treatment group + standard therapy during Period I. During Period II, patients taking Lertal[®] tablets in Period I continue taking one tablet a day for an additional 4 weeks if allergic to pollen or 12 weeks if allergic to dust mites. Lertal[®] is not associated with standard therapy during Period II.

A patient that concludes treatment Period I and still presents symptoms that do not permit suspension of standard therapy is considered a non-responder and will not take part in Period II of the study. The patient will be discontinued from the study and will be treated as deemed appropriate by the Investigator.

Lertal[®] will be provided by the Sponsor free of charge.

9.2 PLACEBO

One placebo tablet identical in appearance, size and taste to Lertal[®] tablets is to be administered daily together with standard therapy (antihistamine) by patients randomized to the placebo + standard treatment group for 4 weeks (Period I only). In Period II, patients taking placebo tablets in Period 1 receive no further treatment.

